**Treatment modifications due to ixazomib-related AEs are outlined in Table (8 and 9).**

Table (8) Ixazomib Treatment Modification (Delays, Reductions, and discontinuations) Due to Adverse Events (Non-Hematologic Toxicities)

Adverse Event (Severity)	Action on Study Drug	Further Considerations
Grade 1 peripheral neuropathy	
 
No action
 
	Grade 1 signs and symptoms: asymptomatic; without pain or loss of function; clinical or diagnostic observations only 
New or worsening Grade 1 peripheral neuropathy with pain or Grade 2	
 
Hold study drug until resolution to Grade <math>\leq</math> 1 or baseline
 
	Grade 2 signs and symptoms: Moderate symptoms; limiting instrumental activities of daily living (ADL) 
New or worsening Grade 2 peripheral neuropathy with pain or Grade 3	
 
Hold study drug until resolution to Grade <math>\leq</math> 1 or baseline
 
Reduce study drug to next lower dose upon recovery
 
	Grade 3 signs and symptoms: severe symptoms; limiting self-care ADL; assistive device indicated 
New or worsening Grade 4 peripheral neuropathy	
 
Discontinue study drug
 
	

Once ixazomib is reduced for any toxicity, the dose may not be re-escalated.

**Table (9) Ixazomib Treatment Modification (Delays, Reductions, and Discontinuations) Due to Adverse Events (Non-Hematologic Toxicities other than peripheral neuropathy)**

Grade 3 nonhematologic toxicity judged to be related to ixazomib	
 
• Hold study drug until resolution to Grade < 1 or baseline
 
	Symptomatic recommendations noted in Section 3.4
If not recovered to < Grade 1 or baseline in one week	
 
• Reduce study drug to next lower dose upon return to < Grade 1 or baseline
 
	
Grade 4 nonhematologic toxicities judged to be related to study drug	
 
• Consider permanently discontinuing study drug
 
	Exceptions are cases in which the investigator determines the patient is obtaining a clinical benefit

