## **3. STUDY DESIGN**

In this phase I study, escalating doses of ixazomib will be combined with a fixed dose VXD regimen. Ixazomib will be administered on day 1, 8, and 15. If the patient experiences a DLT the dose of MLN maybe reduced to the next dose level on day 8 or day 15 in that patient. DLT would be any grade 3 or more toxicity which is

thought to be probably or definitely related to ixazomib. Three patients will be treated per dose level unless dose limiting toxicity (DLT) is observed. The starting dose of ixazomib will be 2.3 mg orally on days 1, 8 and 15. If toxicity is seen at this level then dose may be reduced to 1.5 mg (dose level -1). If no DLT is seen in the first 3 patients, the dose will be increased to 3 mg and then to 4 mg orally on days 1, 8 and 15 in a classic 3 +3 phase I design. The study will not attempt to increase the dose beyond 4 mg orally which, if achieved with acceptable toxicity, would be accepted as the recommended phase 2 dose (RP2D). 0 of 3 DLTs would allow escalation to the next dose level. 1 of 3 DLTs will require expanding to six patients; 1 of 6 DLTs will allow escalation again. Two DLTs will require dose de-escalation. Given that the liver toxicity with the VXLD + ixazomib was attributed to pegaspargase and it is eliminated from this protocol, we will start at dose level 1 of 2.3 mg. The maximum tolerated dose (MTD) will be the highest dose administered at which no more than 1 DLT was observed. All patients will be evaluated for hematopoietic stem cell transplantation. If patients achieve CR and are eligible for HSCT, they will proceed to HSCT. If they are not eligible, no donor is identified or if HSCT will be delayed, and the patient has achieved benefit, then treatment may be repeated at the discretion of the investigator. A total of 9-18 patients will be enrolled on the study. The study duration will be about 2 years. The DLT observation period will be from first dose of MLN9708 to 28 days after the first dose. Dose escalation to a higher dose level will require the last patient on the previous dose level to be out of the DLT observation period.

Patients will be offered an opportunity to provide samples to the institutional bank for use in future research.

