## **7. DOSE-MODIFICATION GUIDELINES**

### **7.1 Recommended ixazomib Criteria for Beginning or Delaying a Subsequent Treatment Cycle & Dose Modifications for Treatment Associated Toxicity**

- Treatment with ixazomib will use a cycle length of 28 days.

All non-hematological toxicity considered to be related to treatment with ixazomib must have resolved to  $\leq$  Grade 1, to the patient's baseline values, or to a level considered acceptable by the physician (eg, hypokalemia that can be managed by replacements) before the next dose of ixazomib could be given. There will be no dose modifications or delays for hematological toxicity as all patients will experience neutropenia and/or thrombocytopenia with the VXD regimen. In the pediatric study, Grade 3 or 4 neutropenia and thrombocytopenia occurred in 97.6 and 79.8% of patients treated with VXLD respectively.

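### The ixazomib hold, resume and reduce rules are inconsistent and have no stated precedence; the painful Grade 1 neuropathy hold is released by its own trigger

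*Combined protocol and SAP*

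**What the plan says.** Several places in the protocol govern the next ixazomib dose after a related non-hematologic toxicity.

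- **Section 7.1, opening text.** The toxicity must have come down to Grade 1 or lower, "to the patient's baseline values, or to a level considered acceptable by the physician", before ixazomib is given again.
- **Table 9 (toxicities other than neuropathy).** A related Grade 3 event is held to a recovery grade, printed as below Grade 1, or to baseline. The next row begins "If not recovered to < Grade 1 or baseline in one week" and its action is "Reduce study drug to next lower dose upon return to" that same level. Neither row leaves the level to the physician. For related Grade 4 events the action is "Consider permanently discontinuing study drug", with an exception for clinical benefit.
- **Table 8 (neuropathy).** One row is triggered by "New or worsening Grade 1 peripheral neuropathy with pain or Grade 2" and is held until Grade 1 or lower, or baseline. Grade 4 neuropathy means discontinuation, with no exception. The table's own description of Grade 1 excludes pain.
- **Section 3.** "If the patient experiences a DLT the dose of MLN maybe reduced to the next dose level on day 8 or day 15". A DLT is any toxicity of Grade 3 or higher that is probably or definitely related to ixazomib.
- **Section 7.5.** A new cycle requires non-hematologic toxicity (alopecia aside) to be at Grade 1 or lower or at baseline, with no physician alternative.

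**The concern.** A related Grade 3 non-hematologic event can fall under Section 3, the opening of Section 7.1 and Table 9 at once. These give different conditions for the next dose, and nothing says which prevails. Two investigators who each follow the protocol could treat the same patient differently after a severe toxicity.

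Patient safety is at stake first. Interpretation comes second: a dose level is judged on three to six patients, and the label of the level is informative only if the dose received is predictable from it. Neuropathy deserves particular care. Section 1.1 raises it as the concern when bortezomib, another proteasome inhibitor, is combined with vincristine, and this regimen gives vincristine on days 1, 8, 15 and 22.

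**Working it through.** The plan gives no figure to reproduce. The check sets the rules side by side for one clinical course and adds up the doses.

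**Inputs.** Dose levels 1.5, 2.3, 3 and 4 mg on days 1, 8 and 15 (Section 5, Table 7). A reduced dose may not be raised again (text under Table 8).

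**Step 1: a course that does not depend on the printed sign in Table 9.** Assume an event of Grade 3 after the day 1 dose, probably or definitely related (so also a DLT), Grade 2 by day 8 and still Grade 2 on day 15, with a baseline below Grade 2 and a physician who accepts Grade 2. Grade 2 fails recovery whether the threshold is below Grade 1 or at most Grade 1.

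| Rule followed | 4 mg level | 3 mg level | 2.3 mg level |
|---|---|---|---|
| Section 7.1, physician accepts | 4+4+4 = 12 mg | 3+3+3 = 9 mg | 2.3+2.3+2.3 = 6.9 mg |
| Section 3 read alone, reduced from day 8 | 4+3+3 = 10 mg | 3+2.3+2.3 = 7.6 mg | 2.3+1.5+1.5 = 5.3 mg |
| Table 9, held on days 8 and 15 | 4+0+0 = 4 mg | 3 mg | 2.3 mg |

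The largest total is three times the smallest: 12/4 = 9/3 = 6.9/2.3 = 3.

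**Step 2: why Grade 1 from day 8 is not used as the example.** With baseline Grade 0 and the sign as printed, Table 9 holds both later doses and gives 4 mg. If the sign should read at most Grade 1, the patient has recovered within the week, no reduction follows, and Table 9 gives 12 mg, the same as Section 7.1. The opening of Section 7.1, Table 8 and Section 7.5 all use at most Grade 1, so the sign needs checking in the protocol file.

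**Step 3: Grade 4 neuropathy, if it is a DLT.** Table 8 discontinues ixazomib. Section 3 read alone permits a lower dose. The clinical-benefit exception in Table 9 does not apply, because that table excludes neuropathy.

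**Step 4: the self-releasing hold in Table 8.** The trigger is Grade 1 with pain and the release is at most Grade 1. Since 1 ≤ 1, the release condition is met when the hold begins. The Grade 2 arm of the same row is not affected, since 2 ≤ 1 is false.

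**Step 5: which patients matter for the dose level.** A Grade 3 event counted as a DLT stays counted whatever is given on days 8 and 15. The unclear exposure lies mainly in patients without a DLT. Grade 2 neuropathy is one case: it is below the DLT grade, Table 8 holds the dose, and Section 7.1 lets the physician give it. One held dose at the 4 mg level leaves 4+4 = 8 mg, less than a full 3 mg cycle (9 mg). One held dose at the 3 mg level leaves 3+3 = 6 mg, less than a full 2.3 mg cycle (6.9 mg). Neither Section 3 nor Section 14.1 sets a minimum exposure for a patient to count toward the DLT assessment.

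**The case against.** The strongest reply is that the rules can be read together. Section 7.1 states a condition that must be met before dosing, not a right to dose. Tables 8 and 9 are introduced as the rules for ixazomib-related events, so the specific tables could be taken to override the general sentence. That would still leave Section 7.1 some work to do, for instance for Grade 2 events other than neuropathy, which Table 9 does not list. Section 3 is permissive and does not waive recovery. This reading is reasonable, and it is why the 10 mg figure is given only for Section 3 read alone. But the protocol never states it, and a site has to infer it after a severe toxicity.

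It is also fair that the DLT definition and Table 9 do not cover identical events. A DLT needs a probable or definite relationship and is not limited to non-hematologic toxicity. The Step 1 example lies where the two overlap.

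On neuropathy, because Table 8 describes Grade 1 as free of pain, its release may be meant as pain-free Grade 1. That is a plausible intention, but the row does not say so.

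A reader might infer more than the documents support:

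- **That a Grade 3 event leads to permanent stopping on some page.** None orders this. Discontinuation arises only at Grade 4.
- **That the MTD call changes through a patient with a DLT.** It does not, for the reason in Step 5.
- **That the whole neuropathy row is without effect.** Only the painful Grade 1 arm releases itself.
- **That the 26% neuropathy rate in Table 1-3 (45 of 173) shows how many patients this affects.** That rate covers all grades, not painful Grade 1.
- **That these are the only safety rules for individual patients.** Section 7.5 sets recovery criteria, Sections 6.1 and 6.2 provide for interruptions and adjustments, Section 13 allows withdrawal for an adverse event, and Section 16.1 requires committee review of each patient.

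**Conclusion.** The inconsistency is real and should be corrected. The opening of Section 7.1 has a physician-acceptable level that Tables 8 and 9 and Section 7.5 lack, Section 3 allows a reduced dose without mentioning hold or recovery, and no order of precedence is given.

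The three-fold spread in Step 1 rests on the assumed course and on each rule being followed by itself. It shows how far the texts can diverge; it does not estimate how often they will. It does not depend on the sign in Table 9. The consequence is inconsistent handling of patients with toxicity and unclear exposure behind a dose-level label. No change in the MTD decision has been demonstrated.

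**What to change.** Reconcile Section 3, the opening of Section 7.1, Tables 8 and 9 and Section 7.5 into one rule set that states:

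- one recovery threshold, given once, with the sign in Table 9 checked against the protocol file;
- whether physician discretion applies to that threshold, and to which events;
- whether a patient with a DLT follows the Section 3 sentence or the sequence in Tables 8 and 9, including for Grade 4 neuropathy;
- which passage prevails if two apply.

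Reword the painful Grade 1 arm in Table 8 so that its release condition differs from its trigger and agrees with the table's description of Grade 1. The clinical thresholds are for the sponsor-investigator to choose; this review takes no view on them.

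The cost is a wording amendment to these sections and tables, with no added patients or procedures.

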## 7.2 Dexamethasone

Hypertension: Dose should not be reduced. Sodium restriction and anti-hypertensives should be employed in an effort to control hypertension. Avoid calcium channel blockers due to their potential prohemorrhagic effect.

Hyperglycemia: Dose should not be reduced for hyperglycemia. Rather, insulin therapy should be employed to control the blood glucose level.

Pancreatitis: Do not modify dose for asymptomatic elevations of amylase and/or lipase. Discontinue steroids, except for stress doses, in the presence of hemorrhagic pancreatitis or severe pancreatitis (abdominal pain > 72 hours and > Grade 3 amylase elevation (> 2.0x ULN)).

Muscle Weakness: Dose may be reduced for grade 2 or 3 muscle weakness.

Osteonecrosis (ON, also referred to as avascular necrosis): Do not modify corticosteroid therapy for osteonecrosis during Induction or Delayed Intensification.

Varicella: Steroids should be held during active infection except during Induction. Do not hold during incubation period following exposure.

Inability to use oral doses:

For dexamethasone, substitute the IV preparation mg for mg.

Severe infection: Do not hold or discontinue steroids during Induction without serious consideration, as this is a critical period in the treatment of ALL.

Severe psychosis: Steroid dose may be decreased by 50% for severe psychosis.

### **7.3 Vincristine**

Severe neuropathic pain (Grade 3 or greater): Hold dose(s). When symptoms subside, resume at 50% previous calculated dose (maximum dose: 1 mg), then escalate to full dose as tolerated. NOTE: neuropathic pain can be not only severe but difficult to treat. However, since vincristine is an important component of curative therapy and the majority of neuropathies are ultimately reversible, vincristine therapy may be given at full dose at investigator discretion. Drugs such as gabapentin may be of value.

Vocal Cord paralysis: Hold dose(s). When symptoms subside, resume at 50% previous calculated dose (maximum dose: 1 mg), then escalate to full dose as tolerated.

Foot Drop, paresis: Should be Grade 3 to consider holding or decreasing dose. These toxicities are largely reversible but over months to years. Accordingly, holding doses of vincristine and/or lowering the dose may not result in rapid resolution of symptoms and may compromise cure. Physical therapy may be beneficial to maintain range of motion and provide AFO's and other forms of support. Drugs such as gabapentin may be of value.

Jaw pain: Treat with analgesics; do not modify vincristine dose.

Hyperbilirubinemia:

Direct bilirubin Dose reduction

< 3.1 mg/dL Full dose (maximum dose: 2 mg)

3.1-5.0 mg/dL 50% of calculated dose (maximum dose: 1 mg)

5.1-6.0 mg/dL 75% of calculated dose (maximum dose: 0.5 mg)

> 6 mg/dL Withhold dose and administer next scheduled dose if toxicity has resolved.

Do not make up missed doses.

Constipation or ileus (> Grade 3) or typhlitis: Hold dose(s); institute aggressive regimen to treat constipation if present. When symptoms abate resume at 50% of calculated dose (maximum dose: 1 mg) and escalate to full dose as tolerated.

Extravasation:

In the event of an extravasation, discontinue the IV administration of the drug and institute appropriate measures to prevent further extravasation and damage according to institutional guidelines. Suggestions below may be helpful but none are considered definitive:

1. Stop infusion, aspirate drug and blood if possible, remove needle.
2. Apply warm compress immediately for 1 hour then rotate on/off every 15 minutes for 24 hours.
3. Hyaluronidase 150 units/mL reconstituted with NS-inject 1 mL for each 1 mL of drug extravasated.

#### **7.4 Criteria for Beginning a Subsequent Treatment Cycle for IT**

- Platelets >30 cmm
- Fibrinogen >100 mg/dL

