### SCHEDULE OF EVENTS

Day	Screening a	Cycle 1 and 2 Week 1	Weekly	Q 2 weeks	Q 4 weeks	End of Study b	Follow-up
Informed consent	X						
Demographics	X						
Inclusion/exclusion criteria	X						
Medical History	X	X					
Medication history	X						
Concomitant medications	X	X		X		X	
Physical examination	X	X		X		X	
ECOG performance status	X	X		X			
Vitals	X	X		X		X	
Height and weight c	X	X d				X	
CBC with differential	X	X	X			X	
Serum Chemistry	X	X	X			X	

panel e							
Direct Bilirubin	X		X				
Fibrinogen	X	X	X				
Serum or urine pregnancy test	X	X f					
Cardiac Ejection Fraction (MUGA/Echocardiogram)	X	x i					
Bone marrow biopsy/aspirate g	X				X	X	
Adverse Event Reporting	Recorded from the first dose of study drug through 30 days after last dose of study drug						
Survival h							X

a Screening procedures to occur up to 14 days before Cycle 1 Week 1 Visit, except for pregnancy test (within 7 days prior to Week 1 Visit).

b Perform end-of-study procedures 4 weeks after study completion or at time of early withdrawal. If study procedure cannot be performed on the scheduled day, the procedure must be performed within 48 hours.

c Height will be measured at Screening only.

d Weight will be checked on day 1 of every cycle

e Including albumin, total protein, total bilirubin, ALT, AST, LDH, alkaline phosphatase, bicarbonate, sodium, potassium, chloride, creatinine, BUN, and glucose.

f Serum  $\beta$ HCG pregnancy test in female patients of childbearing potential does not need to be repeated for Cycle 1 Week 1 Visit if the screening test was completed within 72 hours of Cycle 1 Week 1.

g Bone marrow aspirate and/or biopsy and cytogenetics must be performed within 4 weeks prior to Week 1 Visit. Bone marrow biopsies at week 4  $\pm$ 3 days

h Patients will be followed monthly until progression and then annually for survival.

i For cycle 2 only

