#### **4. STUDY POPULATION**

##### **4.1 Inclusion Criteria**

Each patient must meet all of the following inclusion criteria to be enrolled in the study:

- Male or female patients 18 years or older
- Have relapsed B or T-precursor acute lymphocytic leukemia/lymphoma, lymphoblastic lymphoma or mixed phenotype acute leukemia with increased bone marrow or peripheral blood blasts by morphology with or without CNS involvement
- Prior therapy: At least two prior treatment attempts to induce remission with no limit on the number of prior treatment regimens.
- Patients are eligible after allogeneic stem cell transplantation
- Eastern Cooperative Oncology Group (ECOG) performance status 0-2
- Patients must meet the following clinical laboratory criteria:
  - Total bilirubin  $\leq 1.5 \times$  the upper limit of the normal range (ULN).
  - Alanine aminotransferase (ALT) and aspartate aminotransferase (AST)  $\leq 3 \times$  ULN.
  - Calculated creatinine clearance  $\geq 30$  mL/min
  - Absolute neutrophil count (ANC)  $> 1,000$ /cmm and platelets  $> 75,000$ /cmm unless the cytopenias are secondary to disease
- Life expectancy reasonably adequate for evaluating the treatment effect
- Patients must be at least 2 weeks from major surgery, radiation therapy, participation in other investigational trials and have recovered from clinically significant toxicities of these prior treatments
- Female patients who:
  - Are postmenopausal for at least 1 year before the screening visit, OR
  - Are surgically sterile, OR
  - If they are of childbearing potential, agree to practice 2 effective methods of contraception, at the same time, from the time of signing the informed consent form through 90 days after the last dose of study drug, OR
  - Agree to practice true abstinence when this is in line with the preferred and usual lifestyle of the subject. (Periodic abstinence [eg, calendar, ovulation, symptothermal, post-ovulation methods] and withdrawal are not acceptable methods of contraception.)

- Male patients, even if surgically sterilized (ie, status post-vasectomy), must agree to one of the following:
  - Agree to practice effective barrier contraception during the entire study treatment period and through 90 days after the last dose of study drug, OR

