## **5. TREATMENT PLAN**

All patients will start therapy within 4 weeks from the bone marrow biopsy.

Lumbar puncture with intrathecal chemotherapy will be performed on all patients on day 1 (+/-1 day) to evaluate for disease.

BM or peripheral blood blast will be collected for correlative studies (optional) prior to starting therapy. Details of therapy are as follows:

Vincristine 1.5 mg/m^2 to a maximum dose of 2 mg IV on days 1, 8, 15 and 22

Dexamethasone 10 mg/m^2 orally or intravenously on days 1-14

Doxorubicin 60 mg/m^2 on day 1 by IV bolus.

For patients without CNS involvement:

-Cytarabine 100 mg will be administered intrathecally on day 1 (+/-1 day)  
(cytarabine dose should be reduced to 50 mg if given through a central ommaya reservoir)

-Methotrexate 12 mg will be administered intrathecally on day 8 (+/-1 day)

For patients with CNS involvement:

-Cytarabine 100 mg will be administered intrathecally on day 1 (+/-1 day)  
(cytarabine dose should be reduced to 50 mg if given through a central ommaya reservoir)

-Triple intrathecal chemotherapy with cytarabine 30 mg, methotrexate 15 mg and hydrocortisone 15 mg on (Day 8, 15 and 22 (+/-1 day)).

A bone marrow biopsy/aspirate will be performed at D28 +/- 3 days. For patients in remission, and have an available donor for HCT should proceed to HCT and be removed from the protocol treatment. Patients will still be followed for survival and progression free survival. A second cycle of treatment may be administered at the investigators discretion.

Ixazomib will be administered orally once weekly on day 1, 8 and 15. The first 3 patients will receive 2.3 mg orally (dose level 1). Dose escalation or de-escalation

will then proceed as previously detailed. There will be no inpatient dose escalation.

Table (7) Ixazomib dosing

	Day	Oral Dosing (mg)
Dose level -1	1, 8, 15	1.5
Dose level 1	1, 8, 15	2.3
Dose level 2	1, 8, 15	3
Dose level 3	1, 8, 15	4

Supportive care:

All patients will receive antibacterial, antiviral, antifungal and pneumocystis carinii pneumonia (PCP) prophylaxis. Prophylaxis regimen may follow institutional guidelines. The following prophylaxis may be used as guidelines:

Quinolones for antibacterial prophylaxis e.g., levofloxacin 500 mg orally daily

Antiviral prophylaxis: acyclovir 800 mg orally twice daily

Antifungal prophylaxis: Fluconazole 400 mg orally daily, or Liposomal Amphotericin B 9 mg/kg IV once per week or Caspofungin 50 mg IV /daily

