### **7.5 Criteria for Toxicity Recovery for a New Cycle of Therapy to Begin:**

- Absolute neutrophil count (ANC) > 1,000/cmm and platelets > 75,000/cmm unless the cytopenias are secondary to disease
- All other nonhematologic toxicity (except for alopecia) must have resolved to ≤Grade 1 or to the patient's baseline condition.

If the patient fails to meet the above criteria for retreatment, hold treatment. The patient should be re-evaluated weekly or more frequently to determine whether the criteria for retreatment have been met and a new cycle can begin. If the criteria for retreatment have been met refer to the appropriate drug modification guidelines to resume therapy.

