## 18.2 Response Criteria

CR—M1 (<5% blasts) bone marrow with no evidence of circulating blasts or extramedullary disease and with recovery of peripheral counts (absolute neutrophil count (ANC) >750/ $\mu$ l and platelet count >75,000/ $\mu$ l).

CR without platelet recovery (CRp), M1 bone marrow with no circulating blasts or extramedullary disease and recovery of ANC >750/ $\mu$ l, but insufficient recovery of platelets (<75,000/ $\mu$ l);

Partial remission (PR), complete disappearance of circulating blasts and achievement of M2 (5–25% blasts) marrow status, without new sites of extramedullary disease, and with recovery of absolute neutrophil counts (ANC >750/ $\mu$ l)

Stable disease (SD), does not satisfy the criterion for PD, or has recovery of ANC >750/ $\mu$ l but fails to qualify for CR, CRp, or PR;

Progressive disease (PD), an increase of at least 25% in the absolute number of circulating leukemic cells, development of new sites of extramedullary disease, or other laboratory or clinical evidence of PD, with or without recovery of ANC or platelets.

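### The only platelet limit specific to intrathecal treatment (Section 7.4) lacks its thousands and its per-volume unit and, read literally, would hold back practically no one

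*Combined protocol and SAP*

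**What the plan says.** Section 7.4 is headed "Criteria for Beginning a Subsequent Treatment Cycle for IT" and holds two conditions. The platelet condition is "Platelets >30 cmm". The coagulation condition is "Fibrinogen >100 mg/dL".

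The other platelet limits in the protocol are these:

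- Section 7.5, for starting a new cycle: "platelets > 75,000/cmm unless the cytopenias are secondary to disease".
- Section 4.1 and the Protocol Summary, for entry: 75,000/cmm, with the same exception, "unless the cytopenias are secondary to disease".
- Section 18.2, for complete remission: "and platelet count >75,000" per microlitre.

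Section 5 and Table (2) set the IT drugs, doses and days without a platelet condition. On repeat treatment, Section 5 says "A second cycle of treatment may be administered at the investigators discretion". In the Schedule of Events, "CBC with differential" and fibrinogen are both marked weekly. Section 8.1 leaves platelet transfusion to clinical indication and institutional guidelines.

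**The concern.** The abbreviation cmm on its own is a volume, not a count per volume, so the line as printed is not a usable limit. It sits in operative text that tells staff when a lumbar puncture with chemotherapy may go ahead, and low platelets bear directly on the bleeding risk of that procedure.

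The setting makes low counts likely. Section 7.1 expects neutropenia, thrombocytopenia or both in every patient on the VXD regimen. It cites Grade 3 or 4 thrombocytopenia in 79.8% of children treated with VXLD. That regimen contained pegaspargase, so the figure is context and not an estimate for VXD. Sections 4.1 and 7.5 also lift their own platelet limits when the cytopenia is due to disease. A patient with a low count can therefore be eligible for treatment, and Section 7.4 is the only place where an IT-specific platelet rule could be looked up.

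**Working it through.** This is a check of text and units. No sample size, error rate or other statistical figure is involved, so there is no calculation in the plan to reproduce.

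**Step 1. Put the limits on one scale.** One cubic millimetre equals one microlitre, so /cmm and /µl are the same unit.

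| Place | Purpose | Limit as printed | Complete? |
|---|---|---|---|
| Protocol Summary, 4.1 | Entry | 75,000/cmm | Yes |
| 7.5 | New cycle | 75,000/cmm | Yes |
| 18.2 | Complete remission | 75,000/µl | Yes |
| 7.4 | IT treatment | 30 cmm | No slash, no thousands |

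**Step 2. Compare the two readings of Section 7.4 with Section 7.5.**

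- Literal, 30 per cubic mm: 75,000 / 30 = 2,500. The limit is 2,500 times lower than the one in Section 7.5 and has no practical force.
- Assumed, 30,000/cmm: 30,000 / 75,000 = 0.4. The limit is 40% of the one in Section 7.5, on the same scale as the rest of the protocol. Either a lost 000 with its slash or a lost factor of 1,000 leads to this value.

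**Step 3. Look for the missing value elsewhere.** Section 5 and Table (2) give IT doses and days only. Section 8 restricts platelet transfusion given to meet eligibility criteria within 3 days before study drug dosing, but sets no IT or lumbar puncture limit. Section 8.1 gives no number. Section 7.5 has a number, but it governs the start of a cycle in general, is not specific to IT treatment, and does not apply when the cytopenia is due to disease. None of these supplies the IT limit.

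**Step 4. Could text extraction be the cause?** The fibrinogen line directly below is intact, as are the slash and thousands in Section 7.5, and no redaction is marked. Loss in reading the PDF is unlikely, but it cannot be excluded without the source.

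**Step 5. Trace the effect on the trial's results.** Section 3 defines a dose-limiting toxicity by grade and relation to ixazomib. Section 14.1 plans descriptive summaries of adverse events and a response rate with a 95% confidence interval. Section 18.2 has its own complete platelet limit. None of these uses the Section 7.4 value.

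**The case against.** The best case against the point is that it is editorial. Clinicians would probably read 30,000/cmm, since every other platelet limit is in thousands and 30 per cubic millimetre makes no clinical sense. No rival plausible value is in play, so actual misapplication is not shown. Counts and fibrinogen are checked weekly, and transfusion follows institutional practice. Most of this stands, and it is why the point is minor. It does not remove the error: the documents never state the value, and a safety limit in operative text should not depend on the reader to supply a factor of 1,000.

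A reader might go further and infer that Section 7.4 governs every IT dose, so that most IT doses in each cycle rest on this one faulty line. The documents do not support that. The heading speaks of beginning a subsequent cycle, and Section 5 does not refer to Section 7.4 when it schedules IT treatment. On the heading's wording the line would not reach the first cycle at all. In an optional second cycle, a limit of 30,000/cmm would matter only where the exception in Section 7.5 for disease-related cytopenia applies, because any patient above 75,000/cmm already exceeds 30,000/cmm. Nor do the documents show how many patients fall under that exception, so a count of affected doses cannot be given. What remains is that the scope is unclear.

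**Conclusion.** The point holds as a minor notation error in an operative safety threshold. As printed, the platelet line in Section 7.4 is not a usable limit. Taken literally it is 2,500 times below the Section 7.5 limit, and no other section gives an IT platelet limit.

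Two things are not established. The value 30,000/cmm is an assumption, likely but unstated. The set of IT doses that Section 7.4 covers is open, with the heading favouring the narrow reading, so the practical consequence may be small. There is no effect on the counting of dose-limiting toxicities, the maximum tolerated dose or the analyses. The wording should still be compared with the source file, in case characters were lost there.

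**What to change.** Rewrite the platelet line in Section 7.4 as a full count with its unit, presumably above 30,000/cmm, after the clinical team has confirmed the value against the source. Add one sentence naming the IT doses to which both conditions in Section 7.4 apply. Whether that is only the start of a later cycle or also other doses is a clinical decision, and the correction should not extend the rule by default. The cost is one corrected line and one sentence. No new test is needed, since blood counts and fibrinogen are already scheduled weekly.
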